## **III. Types of research design, principles and experimental steps**

### **1. research design**

This prospective randomized controlled trial was conducted from December 2023 to December 2025 at the Tertiary ICU of Guangdong Second Peoples Hospital, enrolling full-term newborns requiring continuous mechanical ventilation for over 48 hours. Eligible infants were randomly assigned in a 1:1 ratio to receive either conventional position management or LUS-guided position management. The LUS-guided group underwent bedside ultrasound assessments twice daily to monitor atelectasis or consolidation, with position adjustments made based on evaluation results to optimize dependent drainage and ventilation-perfusion matching. Primary outcome was VAP incidence, while secondary outcomes included mechanical ventilation duration, feeding intolerance, pulmonary hemorrhage, pneumothorax, new intracranial hemorrhage, mortality, and ICU length of stay.

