### 1. Selection criteria

All enrolled newborns underwent prospective observation to monitor the incidence of ventilator-associated pneumonia (VAP). VAP diagnosis was based on the criteria established by the U.S. Centers for Disease Control and Prevention (CDC).

 This is indicated for infants under one year of age receiving mechanical ventilation for more than 48 hours. Diagnosis requires: chest imaging demonstrating new or progressive pulmonary infiltrates with deterioration of gas exchange function.

Additionally, at least three of the following clinical or laboratory findings must be present: abnormal body temperature (rectal temperature  $>38^{\circ}\text{C}$  or  $<35.5^{\circ}\text{C}$ ), leukopenia (WBC  $<4\times10^9/\text{L}$ ) or leukocytosis (WBC  $>15\times10^9/\text{L}$ ) with left shift ( $>10\%$  band cells), purulent or increased tracheal secretions, altered sputum characteristics, increased secretions requiring frequent suction, apnea, signs of respiratory distress (tachypnea, chest retractions, wheezing, nasal flaring), abnormal breath sounds (rheumus, crackles, or snoring), bradycardia ( $<100$  bpm) or tachycardia ( $>170$  bpm).

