## **3. Filter criteria**

Participants enrolled in the group who meet one of the following criteria should be excluded:

- (1) Those who do not meet the inclusion criteria or meet the exclusion criteria after inclusion.
- (2) No record.
- (3) Individuals who have not used the trial drug or intervention.

The analysis set is determined by a blind review meeting to exclude cases. The reasons for exclusion should be documented, and the original data should be retained for reference.

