### **Control group (standard positioning management)**

Infants in the control group had their positions adjusted every two hours, alternating between supine, left lateral, right lateral, and prone positions.  The head of the bed should be elevated 15°-30° with the body in a slightly flexed position—hips aligned along the midline, shoulders slightly forward, head centered, and arms

free to move. Position adjustments should only be made when vital signs are stable and resuscitation is delayed, or when adjusting the ventilator, administering IV fluids, or managing deep sleep. If heart rate fluctuates more than 20 beats per minute or SpO2 drops below 90% (excluding airway obstruction), the interval between position adjustments should be extended to 3-4 hours. This group did not undergo ultrasound evaluation.

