## **IX. Data security monitoring**

Clinical trials will establish data safety monitoring plans based on risk levels. All adverse events will be meticulously documented, properly managed, and tracked until resolved or stabilized. Serious adverse events and unexpected incidents must be promptly reported to ethics committees, regulatory authorities, sponsors, and drug regulatory agencies as required. Principal investigators will conduct periodic cumulative reviews of all adverse events, and when necessary, convene investigator meetings to evaluate the risks and benefits of the trial. For double-blind trials, emergency unblinding may be conducted when required to ensure participant safety and rights. Studies exceeding the minimum risk threshold will have independent data monitors assigned to oversee data collection. High-risk studies will establish independent data safety monitoring committees to review cumulative safety and efficacy data, providing recommendations on whether to continue the trial.

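### The VAP primary endpoint has no named or masked assessor although the arms are visible at the bedside; the only blinded step is confined to exclusions

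*Protocol*

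**What the plan says.** - **Endpoint.** Section III.1: "Primary outcome was VAP incidence".
- **Definition.** Section IV.1 requires "chest imaging demonstrating new or progressive pulmonary infiltrates with deterioration of gas exchange function", and in addition "at least three of the following clinical or laboratory findings must be present". The list that follows includes "purulent or increased tracheal secretions, altered sputum characteristics, increased secretions requiring frequent suction, apnea, signs of respiratory distress", then abnormal breath sounds, alongside temperature, white cell count with band forms, and heart rate.
- **Assessor.** On who observes, section IV.1 says only "All enrolled newborns underwent prospective observation to monitor the incidence of ventilator-associated pneumonia (VAP)". It names no diagnosing person, no masked film reader and no adjudication.
- **Blinding.** Section IV.3: "The analysis set is determined by a blind review meeting to exclude cases". The other mention is general wording in section IX, "For double-blind trials, emergency unblinding may be conducted when required to ensure participant safety and rights", which gives nobody in this trial a blinded role.
- **Visibility of the arm.** Section VI has the LUS group scanned at 08:00 and 18:00 and positioned by the findings. Of the control group it says "This group did not undergo ultrasound evaluation".
- **Films.** Section VI schedules chest radiographs on ventilation days 1, 3 and 7 without distinguishing the arms, and allows further films when clinically needed.
- **Image review.** The senior review in the LUS section is a quality check of ultrasound images. It is not a VAP decision and is not stated to be blinded.

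**The concern.** Allocation cannot be hidden from anyone at the cot. When the primary endpoint contains judged items, knowledge of the arm can affect how a borderline infant is labelled. It can also affect whether an extra film is taken and what is charted about secretions or breathing. The measured difference would then mix prevention of pneumonia with labelling of pneumonia, and the chi-square or Fisher test in section X cannot separate the two.

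The protocol does foresee a blinded group looking at cases, but uses it only to decide who is excluded. Who judges the primary endpoint, and what they know, governs how the data are generated. It therefore belongs in the protocol and is not something normally left to an analysis plan.

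**Working it through.** **1. How much of the definition is judged.** Section IV.1 lists nine supporting findings.

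| Type | Findings | Count |
|---|---|---|
| Numeric threshold | temperature; white cells with band forms; heart rate | 3 |
| Judged at the bedside | tracheal secretions; sputum change; suction need; apnea; respiratory distress; breath sounds | 6 |

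Three findings are required, and three of the six judged ones are overlapping secretion items. The supporting threshold can therefore be met by judgement alone. Both mandatory criteria must still be met. They are more objective, but no gas-exchange threshold is fixed, and calling an infiltrate new or progressive is a reading by someone not stated to be masked.

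**2. Inputs for the illustration.** From the protocol: 47 per group (scenario summary), two-sided 0.05, chi-square or Fisher's exact test (section X). The protocol gives no expected VAP rate, so the true rate and the misclassification rates below are assumptions. There is no plan figure on this point to reproduce.

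**3. Counted rates with no true effect, true VAP 20% in both arms.**
- Only error A, 20% of LUS-arm cases uncalled: LUS 0.20 × 0.80 = 0.16; control 0.20.
- A plus error B, 5% of control non-cases over-called: LUS 0.16; control 0.20 + 0.80 × 0.05 = 0.24.

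**4. Rejection rates.** For x control and y LUS cases out of 47 each, X² = 94(x − y)² / [(x + y)(94 − x − y)]. The rejection rate is the sum of Bin(x; 47, pC) × Bin(y; 47, pL) over all tables with p < 0.05. Chi-square is without continuity correction.

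| Scenario | Counted LUS v control | Chi-square | of which favouring LUS | Fisher |
|---|---|---|---|---|
| No lean | 20% v 20% | 5.1% | 2.6% | 2.6% |
| A only | 16% v 20% | 8.3% | 7.5% | 4.4% |
| A and B | 16% v 24% | 16.4% | 16.2% | 10.5% |

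**5. Range over the assumptions (uncalled cases in the LUS arm only, true rate 20% to 50%).**

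| Share uncalled | Chi-square | Fisher |
|---|---|---|
| 0% | 4.8–5.1% | 2.6–3.1% |
| 10% | 5.9–7.6% | 3.0–4.9% |
| 20% | 8.3–16.1% | 4.4–11.5% |
| 30% | 12.6–30.8% | 6.9–23.9% |

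**6. In infants.** Error A alone is 0.20 × 47 = 9.4 against 0.16 × 47 = 7.5 expected cases, about two infants. To turn an exactly equal 14 v 14 into chi-square p < 0.05, eight LUS-arm cases must go uncalled: 14 v 6 gives X² = 94 × 64 / (20 × 74) = 4.06, p = 0.044. Fisher needs nine.

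**The case against.** The strongest reply is that the text is silent and does not assign the diagnosis to unmasked staff. That is correct. A reader might infer that the protocol leaves VAP to people who know the arm, but section IV.1 names nobody. What stands is that no provision separates the decision from knowledge of the arm, so ordinary conduct would leave it with those who can see it.

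Second, a blind review meeting for exclusions is normal practice, and the sentence in section IV.3 contains no error. This is also right. It matters here because it is the only blinded step, and it stops short of the endpoint.

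Third, a reader might infer that VAP rests mainly on bedside impressions. The documents do not support that: no number of secretion or breath-sound findings makes a case without an infiltrate and worse gas exchange, and the scheduled films give both arms the same minimum imaging. These features reduce the exposure. They do not close it, for the reasons in step 1 of the working and because further films follow clinical need.

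Fourth, it is tempting to say that the lean must favour the hypothesis stated in section I. The direction is not fixed. The definition says chest imaging without restricting it to radiographs, and only the LUS arm is scanned twice daily, which could raise detection there and count against LUS.

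Fifth, the figures are assumed. The 8-point gap (16% v 24%) needs two opposite errors at once. With the first error alone and Fisher's test, rejection stays below 5%.

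**Conclusion.** The point holds as a design weakness that should be corrected. The primary endpoint has judged components, no named or masked assessor, and arms that are visible at the bedside, while the protocol's one blinded step is confined to exclusions. Diagnosis may therefore differ by arm, in a direction that cannot be stated in advance.

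The size is unknown. On the assumed 20% true rate with 47 per arm, false rejection by chi-square moves from about 5% to about 8% with one moderate error and about 16% with two. The Fisher figures are about 3%, 4% and 10%. These figures show sensitivity and do not predict what will happen. The finding rests on the text and would stand without them.

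**What to change.** Extend the blind review meeting in section IV.3. Before allocation is revealed, its existing members, where possible those not involved in that infant's bedside care, classify VAP as yes or no and set the onset date for every infant. They work from radiographs, laboratory and ventilator values and charted findings, with arm, position and ultrasound entries removed and the same imaging rule applied in both arms. State in section IV.1 that this classification is the primary endpoint and that the bedside diagnosis is reported as supportive.

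The cost is the preparation of 94 masked files and added meeting time. If existing members do the work, no new staff and no new procedure on the infants are needed. The gain is partial. Findings charted by unmasked staff and extra films taken by clinical need carry any bias into the file, and at a single centre some infants may be recognised. The change reduces the bias without eliminating it, and the report should say so.

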## **4. Drop/Exit criteria**

Drop/Exit criteria:

- (1) The chief physician considers that the clinical condition is not suitable for further experimentation;
- (2) If there is a discrepancy between clinical symptoms and other auxiliary examinations and the results of relevant non-invasive examinations;
- (3) Parents who do not agree to continue the experiment during the experiment

## **5. Termination criteria**

(1) If the following complications occur during the experiment: cardiac arrest, intestinal perforation, intracranial complications, etc.;

- (2) Those who need to be rescued and are not suitable for experimental operations;
- (3) The chief physician considers that the clinical condition is not suitable for further experimentation;
- (4) If there is a discrepancy between clinical symptoms and other auxiliary examinations and the results of relevant non-invasive examinations;
- (5) Parents who refuse to continue the experiment during the experiment

## **V. Research Methods and Technical Routes**

This prospective randomized controlled trial was conducted from December 2023 to December 2025 at the Tertiary ICU of Guangdong Second Peoples Hospital, enrolling full-term newborns requiring continuous mechanical ventilation for over 48 hours. Eligible infants were randomly assigned in a 1:1 ratio to receive either conventional position management or LUS-guided position management. The LUS-guided group underwent bedside ultrasound assessments twice daily to monitor atelectasis or consolidation, with position adjustments made based on evaluation results to optimize dependent drainage and ventilation-perfusion matching. Primary outcome was VAP incidence, while secondary outcomes included mechanical ventilation duration, feeding intolerance, pulmonary hemorrhage, pneumothorax, new intracranial hemorrhage, mortality, and ICU length of stay.

## **VI. Observation items and testing time points**

All infants underwent invasive ventilation using the SLE6000 mechanical ventilator with a heated humidifier via endotracheal intubation, employing disposable respiratory circuits. Both groups received standard NICU care, including standardized VAP prophylaxis, antibiotic therapy when indicated, and routine nursing management in accordance with hospital protocols and international guidelines. Antibiotic selection and adjustment followed local antimicrobial stewardship guidelines, with modifications based on culture and susceptibility test results. On the 1st, 3rd and 7th day of mechanical ventilation, chest radiographs were taken in the positive and lateral positions respectively, and repeated examinations were made according to clinical needs.

### **Control group (standard positioning management)**

Infants in the control group had their positions adjusted every two hours, alternating between supine, left lateral, right lateral, and prone positions.  The head of the bed should be elevated 15°-30° with the body in a slightly flexed position—hips aligned along the midline, shoulders slightly forward, head centered, and arms

free to move. Position adjustments should only be made when vital signs are stable and resuscitation is delayed, or when adjusting the ventilator, administering IV fluids, or managing deep sleep. If heart rate fluctuates more than 20 beats per minute or SpO2 drops below 90% (excluding airway obstruction), the interval between position adjustments should be extended to 3-4 hours. This group did not undergo ultrasound evaluation.

#### LUS Guided Group (Lung Ultrasound Guided Localization)

Postural adjustments follow three principles: ensuring effective drainage of the affected lung area, optimizing ventilation of the healthy area, and preventing stress-related injury  In addition to routine care, two LUS assessments are conducted at fixed times daily (08:00 and 18:00) to guide individualized position adjustments by monitoring regional ventilation.

- If unilateral atelectasis or pulmonary edema is detected, the patient should first be maintained in dependent lateral position for approximately 1 hour, then transition to the contralateral or prone position for 3 hours.
- For lesions previously managed by the department, the prone position duration is reduced to 1 hour, while supine or lateral positions are extended to 3 hours.
- For posterior lesions, the supine or lateral position should be limited to 1 hour, while the prone position should be extended to 3 hours.
- Resume the standard two-hour shift system once the symptoms or edema have subsided.

If SpO2 remains persistently below 90% (excluding operational or feeding disturbances), the respiratory rate increases by more than 20 breaths per minute from baseline, or airway secretions significantly increase, an additional LUS evaluation is required.

All ultrasound examinations are performed by two pediatricians with professional training, while the imaging data undergoes quality review by senior neonatologists with pulmonary ultrasound experience. All physicians receive semi-annual intensive care ultrasound hands-on training from internationally certified instructors to ensure consistent diagnostic standards and standardized technical procedures.

## VII. Criteria for efficacy evaluation

Main efficacy criteria: the effect of lung ultrasound-guided positioning management on the incidence of ventilator-associated pneumonia in mechanical ventilation newborns.

Secondary efficacy criteria included feeding intolerance in newborns, pulmonary hemorrhage, pneumothorax, new intracranial hemorrhage, mortality, duration of invasive mechanical ventilation (from initiation to successful extubation or death), and NICU hospitalization duration.

## **VIII. OBSERVATION OF ADVERSE EVENTS**

Adverse event monitoring: During the trial, clinicians should continuously monitor the child's vital signs. If clinical symptoms or auxiliary findings (e.g., heart rate, liver size, mental status, X-ray, blood gas analysis) contradict non-invasive test results, the trial should be immediately terminated and the attending physician should be promptly consulted.

## **IX. Data security monitoring**

Clinical trials will establish data safety monitoring plans based on risk levels. All adverse events will be meticulously documented, properly managed, and tracked until resolved or stabilized. Serious adverse events and unexpected incidents must be promptly reported to ethics committees, regulatory authorities, sponsors, and drug regulatory agencies as required. Principal investigators will conduct periodic cumulative reviews of all adverse events, and when necessary, convene investigator meetings to evaluate the risks and benefits of the trial. For double-blind trials, emergency unblinding may be conducted when required to ensure participant safety and rights. Studies exceeding the minimum risk threshold will have independent data monitors assigned to oversee data collection. High-risk studies will establish independent data safety monitoring committees to review cumulative safety and efficacy data, providing recommendations on whether to continue the trial.

## **X. Statistical processing**

Statistical analysis was performed using IBM SPSS Statistics (version 20.0; IBM, Inc., Amherst, New York, USA). Continuous variables were presented as mean  $\pm$  standard deviation (SD) or median (interquartile range, IQR) based on their distribution patterns, while categorical data were expressed as frequencies and percentages. Categorical variables were compared using chi-square test or Fisher's exact test, whereas continuous variables were analyzed using independent samples t-test or Mann-Whitney U test as appropriate. A two-tailed P-value  $<0.05$  was considered statistically significant. All procedures were conducted strictly in accordance with the original research protocol.

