## scenario summary

project name	A lung ultrasound-guided strategy for preventing ventilator-associated pneumonia in newborns
purpose of research	This prospective randomized controlled trial, conducted from December 2023 to December 2025, enrolled full-term newborns requiring continuous mechanical ventilation for over 48 hours. The study evaluated whether a lung ultrasound-guided position adjustment strategy could reduce the risk of ventilator-associated pneumonia (VAP) in these infants compared to the traditional empirical position adjustment protocol.
research design	Eligible infants were randomly assigned in a 1:1 ratio to receive either conventional positioning management or LUS-guided positioning management. The LUS-guided group underwent bedside ultrasound assessments twice daily to monitor for atelectasis or consolidation, with positional adjustments made based on findings to optimize dependent drainage and ventilation-perfusion coupling. Primary endpoints included VAP incidence, while secondary endpoints comprised mechanical ventilation duration, feeding intolerance, pulmonary hemorrhage, pneumothorax, new intracranial hemorrhage, mortality, and ICU length of stay.
Total study cases	94 cases (47 cases per group)
Case Selection	Inclusion criteria: Full-term newborns (gestational age 37-42 weeks) requiring continuous mechanical ventilation for over 48 hours. The diagnosis of VAP follows the guidelines established by the U.S. Centers for Disease Control and Prevention (CDC) (18), applicable to infants under one year old receiving mechanical ventilation for more than 48 hours. Diagnosis requires: chest imaging demonstrating new or progressively worsening pulmonary infiltrates, accompanied by deterioration in gas exchange function.

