	
Additionally, at least three of the following clinical or laboratory findings must be present: abnormal body temperature (rectal temperature <math>>38^{\circ}\text{C}</math> or <math><35.5^{\circ}\text{C}</math>), leukopenia (WBC <math><4 \times 10^9 /L</math>) or leukocytosis (WBC <math>>15 \times 10^9 /L</math>) with left shift (<math>>10\%</math> band cells), purulent or increased tracheal secretions, altered sputum characteristics, increased secretions requiring frequent suction, apnea, signs of respiratory distress (tachypnea, chest retractions, wheezing, nasal flaring), abnormal breath sounds, bradycardia (<math><100</math> bpm) or tachycardia (<math>>170</math> bpm).

--	--

	
Exclusion criteria: ① Premature infants; ② Neonates with early-onset sepsis or prior pneumonia; ③ Patients unsuitable for enteral nutrition; ④ Neonates requiring mechanical ventilation for surgical procedures; ⑤ Infants with multiple congenital anomalies or suspected chromosomal abnormalities. Any of these criteria must be met for exclusion from the study.

therapeutic regimen	
All infants underwent invasive ventilation via endotracheal intubation using the SLE6000 mechanical ventilator with a heated humidification system, employing disposable respiratory circuits. Both groups received standard NICU care including standardized VAP prophylaxis, antibiotic therapy when indicated, and routine nursing management in accordance with hospital policies and international guidelines. Antibiotic selection and adjustment followed local antimicrobial stewardship guidelines, with modifications based on culture and susceptibility results. The control group received conventional positioning management, while the LUS-guided group utilized lung ultrasound-guided positioning management.

Efficacy Evaluation	
Effectiveness evaluation indicators (main efficacy indicators and secondary efficacy indicators)
 
Main therapeutic index: the effect of lung ultrasound-guided positioning management on the incidence of ventilator-associated pneumonia in newborns with mechanical ventilation.
 
Secondary efficacy endpoints included feeding intolerance in newborns, pulmonary hemorrhage, pneumothorax, new-onset intracranial hemorrhage, mortality, duration of invasive mechanical ventilation (from initiation to successful extubation or death), and NICU length of stay.
 
Safety evaluation indicators: mortality and complication incidence

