----------------------------	---

Statistical Methods	
Statistical analysis was performed using IBM SPSS Statistics (version 20.0; IBM Corporation, Amherst, New York, USA). Continuous variables were presented as mean <math>\pm</math> standard deviation (SD) or median (interquartile range, IQR) based on their distribution patterns, while categorical data were expressed as frequencies and percentages. Categorical variables were compared using chi-square test or Fishers exact test, whereas continuous variables were analyzed using independent samples t-test or Mann-Whitney U test as appropriate. A two-tailed P-value <math><0.05</math> was considered statistically significant. This analysis strictly followed the original research protocol, with all procedures conducted as planned.

Study duration	From November 1, 2023 to December 31, 2025

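### For uncommon safety events, the one between-arm comparison the protocol fixes (chi-square or Fisher at P<0.05, 47 infants per arm) cannot separate no excess harm from too few infants

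*Protocol*

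**What the plan says.** The synopsis (Efficacy Evaluation) sets safety apart as something to be evaluated: "Safety evaluation indicators: mortality and complication incidence". It does not list the complications. Section VII gives the likely candidates among the secondary endpoints: "Secondary efficacy criteria included feeding intolerance in newborns, pulmonary hemorrhage, pneumothorax, new intracranial hemorrhage, mortality". The trial size is "94 cases (47 cases per group", allocated 1:1.

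Section X, repeated in the synopsis under Statistical Methods, has one rule for all binary outcomes. For description, "categorical data were expressed as frequencies and percentages". For comparison, "Categorical variables were compared using chi-square test or Fisher's exact test", with significance at a two-tailed P below 0.05. Safety outcomes get no rule of their own, and neither place names a risk difference, a ratio, an interval or an upper bound.

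Sections VIII and IX deal with safety during the trial: monitoring of vital signs, recording and follow-up of adverse events, reporting of serious events, and review by the investigators ("Principal investigators will conduct periodic cumulative reviews of all adverse events"). They do not describe an end-of-trial comparison of the arms.

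**The concern.** A two-sided test at 0.05 asks whether the data show a difference. A safety evaluation also has to ask how large an excess of harm the data leave open. When events are few and each arm has 47 infants, a non-significant result is likely whether or not the LUS strategy causes harm, so the P-value says little about that second question.

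The practical risk lies in the final report. A favourable result on ventilator-associated pneumonia could appear beside non-significant comparisons of death, pneumothorax and haemorrhage. The prescribed analysis would contain nothing to show how weak the reassurance is.

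**Working it through.** **Inputs from the protocol.** 47 infants per arm (synopsis); 1:1 allocation (section III); chi-square or Fisher, two-sided 0.05 (section X).

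**Assumptions.** The protocol states no safety event rate, so control rates of 5% to 20% with a doubling in the LUS arm are taken as a range. It does not say when chi-square gives way to Fisher. The usual convention is used: uncorrected chi-square if all expected counts are at least 5, otherwise Fisher. Fisher alone is shown for comparison.

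**The plan's own figure.** The total of 94 cannot be reproduced, because no control rate, target effect, power or dropout is given. It is not called wrong here.

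**Step 1: chance of missing a true harm.** Let a be the control events and b the LUS events. All 48 × 48 pairs (a, b) were enumerated:

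miss rate = 1 − Σ Bin(a; 47, p_C) × Bin(b; 47, p_LUS), summed over pairs with b > a and P < 0.05.

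| Control vs LUS (assumed) | Missed, chi-square/Fisher rule | Missed, Fisher alone |
|---|---|---|
| 5% vs 10% | 92.1% | 94.4% |
| 10% vs 20% | 72.1% | 82.5% |
| 15% vs 30% | 58.4% | 67.6% |
| 20% vs 40% | 42.7% | 51.2% |

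**Step 2: where a doubling stops being missed more often than not.** The miss rate falls below 50% at a control rate of about 18% under the chi-square/Fisher rule (49.1% at 18% vs 36%). With Fisher alone this happens at about 21% (47.9% at 21% vs 42%). Power for a doubling reaches 80% only at a control rate of about 29% to 31%.

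**Step 3: what an interval would show.** The Newcombe interval for d = p_LUS − p_C uses the Wilson limits (l, u) of each arm:

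lower = d − √[(p_LUS − l_LUS)² + (u_C − p_C)²]

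upper = d + √[(u_LUS − p_LUS)² + (p_C − l_C)²]

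Take 7/47 in the LUS arm and 2/47 in control:

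- p_LUS = 0.1489, Wilson limits 0.0741 to 0.2769
- p_C = 0.0426, Wilson limits 0.0117 to 0.1425
- d = 5/47 = 0.1064
- lower = 0.1064 − √(0.0748² + 0.0999²) = 0.1064 − 0.1248 = −0.018
- upper = 0.1064 + √(0.1280² + 0.0309²) = 0.1064 + 0.1317 = +0.238

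The expected event count is (7 + 2)/2 = 4.5 per arm, so Fisher applies and P = 0.16. By the stated rule this is non-significant, yet the data are compatible with an excess of nearly 24 percentage points.

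Other illustrative counts (LUS vs control):

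| Events | Fisher P | Difference, points | 95% Newcombe interval, points |
|---|---|---|---|
| 0/47 vs 0/47 | 1.0 | 0 | −7.6 to +7.6 |
| 2/47 vs 2/47 | 1.0 | 0 | −10.5 to +10.5 |
| 6/47 vs 3/47 | 0.49 | +6.4 | −6.4 to +19.5 |
| 10/47 vs 5/47 | 0.26 | +10.6 | −4.5 to +25.5 |

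In the last row the expected count is 7.5 per arm, so the convention would select chi-square (P = 0.16), which is also non-significant.

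**The case against.** The strongest reply is that this is an absence rather than an error. Chi-square and Fisher are valid tests for binary outcomes, section X is a general paragraph that does not forbid intervals, and a statistical analysis plan that is not shown may add them. That stands as far as it goes: missing intervals alone would not be a finding. But the protocol does not leave the matter open. It states a comparison rule twice and applies it to every categorical variable, including those it calls safety indicators, and for uncommon events that rule tells the reader little.

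Stronger readings are tempting, and the documents do not support them:

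- **That the protocol will treat P≥0.05 as proof of equal safety.** A reader might infer this, but no sentence says it, and the objectives and hypothesis contain no equivalence or non-inferiority claim about safety.
- **That safety is judged only by significance tests.** Section X also gives counts and percentages, and sections VIII and IX set out monitoring and cumulative review. The point is confined to the end-of-trial comparison between arms.
- **That a doubling of any harm would usually be missed.** This depends on rates the protocol does not give. It fails above a control rate of about 18-20%, which could include a common complication such as feeding intolerance.
- **That the LUS arm abandons two-hourly turning for longer holds and so carries a known extra risk.** Section VI applies the 1-hour and 3-hour timings when ultrasound finds a lesion, in addition to routine care, and then returns to the two-hour schedule. The control arm may itself extend to 3-4 hours. The Background's remark on haemodynamic instability concerns frequent repositioning, so it does not show added risk from longer holds.

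It is also fair to say that the fix supplies no harm margin and so yields no pass/fail decision. Its purpose is to report what the data leave open.

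**Conclusion.** The point holds in limited form, as a cheap improvement rather than a fault in the trial's design. With 47 infants per arm, the stated comparison for mortality and complications cannot distinguish no excess harm from too little information when events are uncommon. For control rates of 5%, 10% and 15%, a true doubling is missed about 92%, 72% and 58% of the time. At 20% the figure is 43% under the chi-square/Fisher rule and 51% with Fisher alone, so the statement should not be extended to common events. The figures rest on the assumed event rates, the expected-count convention for choosing the test, and all 94 infants being analysed.

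**What to change.** In section X and in the synopsis Statistical Methods, add two or three sentences for mortality and each complication:

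- Report events/N per arm and the risk difference (LUS minus control) with a 95% Newcombe or Miettinen-Nurminen interval.
- Word the safety statement from the upper limit, meaning the largest excess risk that the data do not rule out.
- State that P≥0.05 on a safety indicator is not evidence of equal safety.

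If a statistical analysis plan exists, it should carry the same wording. The intervals come from counts already collected, and neither the sample size nor the conduct of the trial changes. The cost is a less favourable safety statement, because the intervals will be wide: even no events in either arm leaves an upper limit of 7.6 points.
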